The focus of this project is physical activity and sedentary behavior, yet dietary intake is a critical component to energy balance and weight gain.4.15 Therefore, dietary intake will be assessed to characterize children's energy balance so that the effects of physical activity and sedentary behavior on obesity can be isolated from dietary intake. Dietary intake will be monitored by the NCI Selfadministered 24-hour Dietary Recall (ASA24 TM). The 24-hour dietary recall is considered the gold standard to assess free-living diet in children.69 The ASA24™, which has been used in over 300 clinical trials,70 was developed to be automated and self-administered, enabling the efficient administration of multiple recalls in large-scale epidemiological studies such as the present study. The format and design are adapted from the interviewer-administered Automated Multiple-Pass Method (AMPM) developed by the USDA. The ASA24[™] has been validated with 80% accuracy vs. 83% in AMPM, based on inconspicuous observation of adults consuming an ad libitum buffet meal.71 Parents will assist children in completing the instrument, and trained staff will be available to answer questions. Participants will complete the ASA24 survey outside of clinic two more times at each visit time point within approximately one week of the completed clinic visit. Surveys will be completed twice on a week day and once on a weekend at Year 0 and again at Year 2. Dietary patterns derived from principal components analysis will be used as a covariate and tested as a mediator in the proposed analyses.

Accelerometer

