The hypotheses will be tested using a series of generalized linear models with severe obesity as the independent variable. First, linear mixed effect models will be used to test for effects between BMIz and each dependent continuous variable (change in: min/day sedentary behavior, min/day MVPA, and each cardiometabolic risk factor). Next, logistic regression models will be used to determine the association between BMIz with the likelihood of not meeting recommended behaviors (i.e. top quartile of min/day of sedentary behavior; MVPA < 60 min/day) or being at elevated cardiometabolic risk. Finally, the cohort will be stratified into two groups based on obesity at Year 0: severely obese (SO) and not severely obese (NSO). Logistic regression models will be used to determine associations between SO (vs. NSO) and each dependent variable (i.e. change in: minutes/day sedentary time, minutes/day MVPA, and each continuous cardiometabolic risk factor). Covariates will include age, sex, dietary intake, and race. School

term vs. school holiday will be considered as an additional covariate if time of year is significantly associated with the independent and dependent variables.

Secondary analysis will use MRI and DXA as covariates in the model (namely the visceral, trunk, and total body fat). These measurements, along with BMIz, may be highly correlated. Various variable select criteria (including LASSO and support vector machine) will be used to determine which combination of these variables best explains the variance in the data. The full model will enable the comparison of imaging-based body composition measures vs. BMIz alone and their associations with physical activity, sedentary behavior, and cardiometabolic risk factors in children.

As exploratory analyses, dietary intake will be tested as a potential mediator to explain significant associations between the predictor variable (BMIz) on outcomes (physical activity, sedentary behavior, and cardiometabolic risk factors). Series of sequential models will be used to test each pathway using a path analysis model based on the Baron and Kenny causal steps for mediation.73,74

Objective 2:

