The primary outcome for the first objective is change in minutes of sedentary behavior between Year 0 and Year 2 (i.e. Year 2 values minus Year 0 values). Baseline estimates for the two groups were calculated using the WAIST cohort data (from the 2010-11 assessment). Based on data from Berkey et al.,75 the SO group is assumed to increase their sedentary time by 30 minutes/day at year 2, while smaller increases in sedentary time is expected for the NSO group (**Table 5**). A minimum of 334 participants is needed to ensure a well-powered study with significance level of $\alpha = 0.05$, 80% power to detect a 24 minute difference change in sedentary behavior between the two groups, and allowing for a dropout rate of 25%. Therefore, our sample size of up to 345 participants will be sufficient.

Change in minutes/day of sedentary time for NSO group	Change in minutes/day of sedentary time for SO group	Difference in change between groups	Standard deviation of change between groups	Minimum sample size	Total sample size (allows for 25% dropout)
2.4	30.0	27.6	69.6	202	253
3.6	30.0	26.4	69.6	222	278
4.8	30.0	25.2	69.6	242	303
6.0	30.0	24.0	69.6	266	334

Table 5. Difference in changes in sedentary time based on severe obesity status. *Note.* NSO is the group classified as not severely obese; SO is the group classified as severely obese.

Note. NSO is the group classified as not severely obese; SO is the group classified as severely obese.

Secondary analyses will include change in daily MVPA minutes between years and change in days/week of physical activity (\geq 60 minutes MVPA/day) between years. Power analysis was conducted on these outcomes, using the WAIST cohort and data from Nigg et al.,76 and our sample size will have power of 93.8% and 90.4% to detect a significant difference in change in daily MVPA minutes and change in days/week of physical activity, respectively.

Contingencies

Based on national reference data, it is possible that very few or no severely obese children meet the healthy behavior or cardiometabolic health criteria (e.g. no severely obese child attains ≥ 60 minutes of MVPA/day; no severely obese child has a waist circumference < 90th percentile). If this is the case, the dichotomous dependent variable will be adjusted to be quartiles, so that the analyses is interpreted as the likelihood of a severely obese child being in the top (healthiest) quartile of the health behavior or cardiometabolic health criteria for the overall cohort.

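### Diet is tested as a mediator only where the BMIz association is already significant, by the causal steps, with no planned indirect effect or interval

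*Combined protocol and SAP*

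**What the plan says.** Under Statistical Analysis, Objective 1, the last paragraph states: "As exploratory analyses, dietary intake will be tested as a potential mediator to explain significant associations between the predictor variable (BMIz) on outcomes". The outcomes are physical activity, sedentary behavior and cardiometabolic risk factors. Each pathway is to be tested in a series of models, "using a path analysis model based on the Baron and Kenny causal steps for mediation". No product of coefficients, bootstrap or confidence interval for an indirect effect is named anywhere, and no power is given for mediation.

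Two other places give diet a second role. The covariate list for the Objective 1 models reads "Covariates will include age, sex, dietary intake, and race". The 24-hour Dietary Recall section says "Dietary patterns derived from principal components analysis will be used as a covariate and tested as a mediator in the proposed analyses". The plan does not say whether the association that must be significant comes from a model with or without diet.

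**The concern.** The quantity of interest in a mediation analysis is the indirect effect: the BMIz-diet path multiplied by the diet-outcome path. The causal steps replace its estimate with a sequence of yes/no tests, the first of which is that BMIz and the outcome are significantly associated. If that association is modest, or if direct and indirect paths partly cancel, mediation is never examined, even when both component paths are clear. The reader is then left without an effect size or its uncertainty.

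The dual role of diet adds an ambiguity. If the gate is read from the covariate-adjusted Objective 1 model, it tests the association that remains after removing the part passing through diet, which is the part the mediation analysis is meant to find.

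**Working it through.** **The plan's own figure.** Power analysis, Objective 1, asks for "80% power to detect a 24 minute difference change in sedentary behavior between the two groups", with the Table 5 row "24.0 69.6 266 334". Two-sided 5% and equal groups are assumed: n per group = 2 × (1.96 + 0.8416)² × (69.6/24)² = 2 × 7.849 × 8.41 = 132.0, rounded up to 133, so 266 in total. This matches.

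**Total effect as a correlation.** d = 24/69.6 = 0.345; r = d/√(d² + 4) = 0.17. This carries the severe versus not severe contrast over to continuous BMIz, which is an approximation.

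**Sample sizes.** The maximum is 345. With the combined 25% dropout, 345 × 0.75 gives about 258. With only the 13% loss to follow-up, 345 × 0.87 gives about 300. The full 345 is the upper bound.

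**Power of the gate.** Φ(d√n/2 − 1.96) = 0.79 at n=258, 0.85 at n=300 and 0.89 at n=345. Even at the planned effect, the gate therefore closes in about one study in five at n=258.

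**Path sizes (assumptions; the documents give none).** Let a be BMIz to diet, b diet to outcome given BMIz, and c′ the direct effect, all standardized. Take a = b = 0.20. For a total effect of 0.17, c′ = 0.17 − 0.20 × 0.20 = 0.13.

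**Hand check.**
- SE(a) ≈ √(0.96/(n − 2)).
- Residual variance of the outcome = 1 − (0.04 + 0.0169 + 0.0104) = 0.933, so SE(b) ≈ √(0.933/(0.96n)).
- At n=258 both standard errors are about 0.061, and each path has power of about 0.90. Both are significant in about 0.82.
- Treating the gate as roughly independent of the two paths, causal-steps power ≈ 0.79 × 0.82 = 0.65.

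This was compared with simulation (2,000 data sets per setting; repeated runs differ by a few points):

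| n | Gate | a and b both | Gate × both | Simulated causal steps | Simulated test of a×b | Loss (points) |
|---|---|---|---|---|---|---|
| 258 | 0.79 | 0.82 | 0.65 | 63–66% | 78–81% | about 15 |
| 300 | 0.85 | 0.88 | 0.75 | 72–75% | 88% | 13–16 |
| 345 | 0.89 | 0.93 | 0.83 | 83% | 92–93% | 10–11 |

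Joint significance of a and b comes within 3 points of the Monte Carlo interval for a×b. The loss therefore comes from the gate, not from testing the paths one at a time. The interval does not gain its power through false positives: with a = 0, b = 0.26 and n=258 it excluded zero in 5% of runs.

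**Other assumed paths, n=258, causal steps versus test of a×b:**
- Planned total effect, a = b = 0.26: 75% vs 97%.
- Direct effect 0.14: 28% vs 37% (a = b = 0.14), 67% vs 80% (0.20), 89% vs 97% (0.26).
- No direct effect, a = b = 0.20, so total 0.04: 8% vs 79%.
- Opposing direct effect −0.10: 13% vs 81% (0.20), 8% vs 98% (0.26).

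**If the gate is adjusted for diet.** It then tests c′. At the planned effect with paths of 0.20 and n=258, SE(c′) ≈ √(0.933/(0.96 × 258)) = 0.061, z = 0.13/0.061 = 2.1, and power is about 0.56. Multiplied by 0.82 this gives about 0.46; simulation gives 43 to 45%. The direction is not universal: when c′ opposes the indirect path, c′ can be larger in size than the total effect, and the adjusted gate then opens more often.

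The simulation omits covariates, error in the dietary recalls and multiple dietary components.

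**The case against.** Several points on the other side stand.

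- A path analysis gives both coefficients and hence their product. A reader might infer that the plan cannot yield an indirect-effect estimate; the text does not support that. It only fails to commit to reporting one with an interval.
- A reader might infer that power collapses to about 8%. That figure needs a total effect of 0.04, where the gate itself has only about 10% power. The plan is built on about 0.17, where the loss is about 15 points.
- A reader might also expect a false conclusion that diet does not mediate. At the planned effect the causal steps succeed in roughly 63 to 75% of studies at n=258, depending on the paths. Where the gate closes, the text implies that mediation is not examined, not that a negative result is declared.
- The 25% dropout includes 12 points for scanner weight limits and refused procedures such as MRI or DXA. BMIz, diet and activity do not need scans, so about 300 may be the better sample size.
- Explaining associations that have been observed is a legitimate, narrower question. Removing the gate adds comparisons across dietary components and outcomes.

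These points reduce the size and severity. They do not supply the missing interval, or say which model sets the gate.

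**Conclusion.** The point holds as a minor one. The plan limits mediation to significant associations, decides it by the causal steps, and commits to no indirect effect with an interval. At the plan's own total effect and assumed paths of 0.20, the gate costs about 15 points of power at n=258 (63% vs 78%), about 13 at n=300 and about 11 at n=345. Losses reach 68 to 90 points with a direct effect of −0.10, but only under path sizes the documents neither state nor imply. If the gating model includes diet, power at the planned effect is about 43% at n=258; the plan leaves this open.

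A stronger inference, that Objective 1 itself is undermined, is not supported. The analysis is labelled exploratory, and no stated hypothesis, primary outcome or sample size rests on it.

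**What to change.** Replace the causal-steps sentence in the Objective 1 exploratory analyses with the following:

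- For sedentary time, MVPA and each cardiometabolic factor, estimate the product of the BMIz-diet and diet-outcome coefficients for each retained dietary component, with a percentile-bootstrap or Monte Carlo 95% interval, whether or not the total association is significant.
- Fit the total-effect model without dietary intake, and state this explicitly.
- Drop the causal-steps decision rule and keep the exploratory label.
- Report the intervals as estimates, without claims of significance.

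The cost is a few sentences in the analysis plan and some computing time. No extra participants, visits or measurements are needed. The one downside is more comparisons, which the last item addresses.

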We will include adolescents aged 10 to 16 years. We selected this age range because adolescence is a developmental period of rapid fat gain and changes in activity patterns. By choosing the maximum age as 16 years at baseline, the children are likely to still live in Baton Rouge and attend high school at the second clinic visit (age 18 years), facilitating follow-up.

Inclusion Criteria:

- Age 10-16 years
- Body weight < 500 lbs.
- Ability to understand instructions and complete all study procedures

Exclusion Criteria:

- Pregnant
- On a restrictive diet due to illness
- Significant physical or mental disabilities that impede walking, wearing accelerometer or GPS, or responding to EMA.

In addition to the exclusion criteria listed above, participants who refuse to provide written assent, or whose parents or legally authorized representative refuse to sign an informed consent document, will be excluded from the study. Consent/assent will be obtained upon each participant's arrival at the PBRC Pediatric Research Clinic before participating in any study procedures. To further safeguard participant safety and internal validity of the study, inclusion and exclusion criteria will be reassessed by PBRC clinic staff following the completion of required assent/consent forms. The principal investigator and medical investigator have the right to withdraw a participant from the study at any point for any reason.

Number of Participants

We will identify and recruit up to 345 boys and girls aged 10 to 16 years. The sample will be screened on the telephone in attempt to achieve a comparable sex and race distribution. We will oversample for severely obese youth so they comprise approximately 50% of the sample (with the other 50% being distributed among normal weight, overweight, and obese status).

Recruitment Methods

Recruiting children for clinical studies is challenging, particularly those from high risk populations such as with severe obesity and from ethnic minority groups. However, we are confident we can recruit up to 345 children within 2 years. A key recruitment strategy will be to enroll participants who completed the WAIST Study.¹⁶ Of 423 initial participants who were assessed for the WAIST Study in 2010-11, 386 (91.3%) agreed to be re-contacted. Of these, 193 participants will meet the age criteria for the follow-up

Page 7 of 35

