We will conduct a prospective epidemiological study to determine the effect of severe obesity on physical activity, sedentary behavior, and cardiometabolic risk factors among African American and White children and adolescents. Physical activity, sedentary behavior, cardiometabolic risk factors, and body composition will be assessed in each participant using gold standard, objective measures, with the first assessment (Year 0) in 2016-17 and the second assessment (Year 2) in 2018-19. We previously observed that children's physical activity and other health behaviors vary throughout the year based on school term versus school holiday.⁶⁰ Therefore, each child's Year 0 and Year 2 clinic visits will be scheduled at a consistent time of year to protect against changes due to the child being in school term or on a school holiday. Furthermore, we will use a scheduled enrollment to ensure that clinic visits are representative of both school term and school holidays.

Following an initial recruitment telephone screen or web-screen (followed by a telephone screen) to assess initial eligibility criteria, eligible participants will be scheduled for their Orientation visit at PBRC with their parent or legally authorized representative where participants will be formally oriented to the study by receiving detailed information on the purposes, goals, procedures, participant flow, and study timeline. Staff will obtain signed informed consent and child assent before participants take part in any of the study-related procedures. Participants will be given the GPS and accelerometer devices as well as instructions on how to wear them for the next week. Participants will also be given the EMA application on their personal cell phones or a provided mobile device along with instructions on how to respond to the prompts for the next week. Participants will be introduced to the ASA-24 dietary intake tool and provided instructions on how to complete two separate recalls from their home computer prior to the Year 0 clinic visit. Participants and parents may be asked to complete surveys on the devices while waiting. At the conclusion of the Orientation. Parents may receive reminders from staff for all tasks required of participants between orientation and Year 0.

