Participants will be fasting at the Year 0 visit. Measurements including anthropometry, blood draw, urine pregnancy test, body composition, dietary intake, activity monitor tracking equipment collection, and all remaining surveys will take place during the clinic visits. Participants must be accompanied by a parent or legally authorized representative at the clinic visits.

Approximately 10 days prior to the Year 2 visit, participants will pick up an accelerometer and GPS device to wear for 7 days and return at the Year 2 clinic visit. Participants will also be given instructions on how to complete two trials of the ASA-24 dietary intake tool from their home computer prior to the Year 2 clinic visit. Participants will return to clinic approximately 2 years (+/- 6 months) after their Year 0 visit for a Year 2 visit, in which all procedures collected during Year 0 will be repeated. **Table 2** includes a list of all measurements occurring at both visits. Parents may receive reminders from staff for all tasks required of participants between orientation and Year 2.

Measurements

	Orientation	Year 0	Year 2
Informed consent/assent	Х		
Anthropometry (Height, weight, waist size)		Х	Х
Blood Pressure		Х	Х
Body Composition (DXA, MRI)		Х	Х
Blood Draw		Х	Х
Urine Pregnancy Test (eligible females only)		Х	Х
Dietary Intake (ASA-24)		Х	Х
Family environment surveys		Х	Х
Neighborhood environment surveys		Х	Х
Body image and mood surveys		Х	Х
Global Positioning System (GPS)	7-days		7-days
Physical Activity (Actigraph GT3X+)	7-days		7-days
Ecological momentary assessment (eMA)	7-days		

Table 2. Study procedures

Description of tests and procedures

Anthropometry

Weight- Anthropometry will be measured to the nearest 0.1 cm (0.1 kg for weight). All measures are taken twice with the analyzed value being the average of both measurements. If the measures differ by greater than 0.5 units, a third measurement will be taken to replace the discrepant value. Participants wear only a hospital gown and undergarments while being weighed.

Height- Standing height will be measured using a Harpenden stadiometer (Holtain Limited, Crymych, UK). Participants will remove shoes, stand upright with heels and back against the stadiometer, inhale, and hold breath while an assessor provides traction to align the participant's head along the Frankfort Horizontal Plane during measurement. Weight will be measured using a Michelli GSE 460 scale (G.T. Michelli Co., Baton Rouge, LA).

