Analyses to test Hypothesis 2 will be conducted using a series of linear regression models (i.e. linear mixed effects models). Based on difference score between Years 0 and 2 for total body fat, the group will be divided into two dichotomous groups using percentiles: high fat gainer (HFG) and low fat gainer (LFG). These variables will be used to predict changes in physical activity, sedentary behavior, and each cardiometabolic risk factor in linear mixed effect models. Covariates will include age, sex, dietary intake, and race. School term vs. school holiday will be considered as an additional covariate if time of year is significantly associated with the independent and dependent variables. Secondary analysis will use MRI and DXA as covariates in the model (namely the visceral, trunk, and total body fat). As previously reported, variable select criteria (including LASSO and support vector machine) will be used to determine which combination of these variables best explains the variance in the data. The full model will enable the comparison the accumulation of imaging-based body composition measures vs. BMIz alone and their associations with change in physical activity, sedentary behavior, and cardiometabolic risk factors in children. Finally, there are no standard accepted definitions of pediatric severe obesity to dichotomize participants based on MRI or DXA measures of body fat. Therefore, receiver operating characteristic curves will be created to estimate the value at which visceral, trunk, and body fat best correspond with the BMI definition of severe obesity (i.e. $BMI \ge 120\%$ of the 95th percentile1). Clinically relevant cut-points of severe obesity based on total, trunk, and visceral body fat will be established among this diverse cohort of adolescents.

Power analysis

Objective 1:

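### Objective 2 uses raw Year 2 minus Year 0 differences over an 18-to-30-month visit window with no elapsed-time term, a small and avoidable bias towards Hypothesis 2

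*Combined protocol and SAP*

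**What the plan says.** Under Study Design, the follow-up window is: "Participants will return to clinic approximately 2 years (+/- 6 months) after their Year 0 visit for a Year 2 visit". The same section says that "each child's Year 0 and Year 2 clinic visits will be scheduled at a consistent time of year"; the reason given is to avoid differences between school term and school holiday.

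Under Statistical Analysis, Objective 2, the exposure is built from an unscaled change: "Based on difference score between Years 0 and 2 for total body fat, the group will be divided into two dichotomous groups". The percentile used for the split is not stated. The groups then predict changes in physical activity, sedentary behaviour and cardiometabolic factors. The adjustment set is: "Covariates will include age, sex, dietary intake, and race". There is one conditional addition: "School term vs. school holiday will be considered as an additional covariate if time of year is significantly associated" with the independent and dependent variables.

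The Objective 1 power section defines the outcome as "change in minutes of sedentary behavior between Year 0 and Year 2 (i.e. Year 2 values minus Year 0 values"). Objective 2 takes change in sedentary behaviour as its primary outcome too. Neither document section annualises a change or enters the time between visits into a model.

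**The concern.** The window allows a 1.67-fold spread in follow-up (30/18 months). A raw difference mixes a child's rate of change with the length of time observed. The plan itself gives both variables an upward trend. The eligibility rationale says that "adolescence is a developmental period of rapid fat gain and changes in activity patterns", and Tables 5 and 6 assume that sedentary time increases in every group.

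Elapsed time therefore pushes exposure and outcome in the same direction. Two children gaining fat at the same yearly rate can land in different groups because one was seen later, and the later child's sedentary time has had longer to rise. This creates a positive HFG-LFG difference even with no true link, in the primary analysis of Objective 2 and in the direction that Hypothesis 2 predicts. It also misclassifies some children on the exposure.

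The listed covariates do not absorb this. A single age term does not measure months between visits, term versus holiday is season and not duration, and a mixed model fitted to one change score per child contains no visit time.

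**Working it through.** **1. The plan's own figure.** Table 6 gives a difference of 8.4 min/day, SD 24, minimum N 255 and a total of up to 345. With two-sided alpha 0.05, 80% power and equal groups (assumed, because the split is not stated):

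n per group = 2 × (1.96 + 0.84)² × 24² / 8.4² = 128.1, so 129 per group and 258 in total, against 255 stated. Allowing 25% dropout, 255/0.75 = 340, against up to 345. With 345 × 0.75 = 258.75 evaluable, power is 80.4%. The planning figure is reproduced and is not in dispute.

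**2. Sedentary slopes from the documents.**
- Table 6, 8.4 row: HFG +12 and LFG +3.6 over two years. Mean (12 + 3.6)/2 = 7.8, or 3.9 min/day per year.
- Table 5, 24.0 row: severely obese (SO) +30 and not severely obese (NSO) +6.0 over two years. Mean 18, or 9 min/day per year.

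**3. Assumptions, not in the documents.** Yearly fat gain is normal with mean/SD of 2.5/2.0, 3/1.5 or 4/3 kg, independent of visit timing. Fat gain = yearly rate × elapsed years T. The split is at the median. There is no true association between fat gain and sedentary change. The distribution of T is varied.

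**4. Formula.** Spurious difference = slope × (mean T in HFG − mean T in LFG), from 2,000,000 simulated children per scenario.

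For visits uniform over 18-30 months, the mean T differences are 0.083, 0.131 and 0.089 years (1.0 to 1.6 months):
- at 3.9 per year: 0.32, 0.51 and 0.35 min/day, or 3.9%, 6.1% and 4.1% of 8.4;
- at 9 per year: 0.75, 1.18 and 0.80 min/day, or 8.9%, 14.0% and 9.5% of 8.4;
- children who change group compared with a split on yearly rate: 6.3%, 9.9% and 6.7%.

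**5. Sensitivity to visit timing** (range over the three fat-gain scenarios):

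| Visit times | Bias at 3.9/yr (min/day) | Bias at 9/yr (min/day) | Change group |
|---|---|---|---|
| Uniform 18-30 months | 0.32-0.51 | 0.75-1.18 | 6-10% |
| Triangular 18-30, peak at 24 | 0.16-0.26 | 0.37-0.60 | 4-7% |
| Uniform 21-27 months | 0.08-0.13 | 0.18-0.30 | 3-5% |
| Uniform 22-26 months | 0.04-0.06 | 0.08-0.13 | 2-3% |

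**6. Effect on the test.** With 258 evaluable, SE = 2 × 24/√258 = 2.99 min/day. Under uniform 18-30 months, a bias of 0.32-0.51 is 0.11-0.17 SE, and two-sided type I error is 0.051-0.053. At the 9 per year slope it is 0.057-0.068, falling to 0.052-0.055 with the triangular spread.

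**7. Upper limit.** If every child gained fat at the same rate, elapsed time alone would decide the group. HFG would then be seen 0.5 years later, giving 0.5 × 3.9 = 1.95 min/day (23% of 8.4) at Table 6's slope and 0.5 × 9 = 4.5 (54%) at Table 5's mean slope.

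**The case against.** The strongest reply is that visits will not spread evenly over the window. Visits are to fall at a consistent time of year, which sits badly with a return at 18 or 30 months, and the Retention section adds a scheduling call two months before the Year 2 visit. The target is 24 months and the six months either side is an outer tolerance. This stands in part: it makes the uniform case the wide end of the range. But the scheduling rule is aimed at term versus holiday, and a term-time visit some months off target still satisfies that aim. It narrows the spread without removing it.

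The second reply is that the fat-gain figures and the distribution of visit times are assumed. That is correct, which is why a range is shown. Total body fat is also not specified as kilograms or percent. Percent fat need not rise in every child, and the bias would then be weaker.

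Three stronger readings are tempting, and the documents do not support them:
- A reader might apply Table 5's SO slope (30/2 = 15 min/day per year) to everyone and report 1.3-2.0 min/day, 15-23% of 8.4. Only about half the sample is to be severely obese, and Table 5's NSO group rises far more slowly. Setting that slope against Table 6's target inflates the percentage nearly fourfold (15/3.9 = 3.8).
- A reader might infer that visit timing could produce the planned 8.4 min/day by itself. Even the upper limits above fall well short.
- A reader might extend the bias to Objective 1, for example by supposing that SO children return three months later (0.25 × 15 = 3.75 min/day). Exposure there is Year 0 status, so elapsed time does not help to form the groups. Nothing in the documents indicates that SO and NSO children return at different times.

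**Conclusion.** The point holds for Objective 2 as a small, avoidable bias towards the hypothesis, and not as a threat to the study. The window, the raw differences and the missing interval term are all in the text, and the direction follows from the plan's own expectation that fat and sedentary time rise. The most consistent size sets Table 6's slope against Table 6's target: about 0.3-0.5 min/day, 4-6% of 8.4, with type I error barely above 0.05. Using Table 5's two-group mean slope it is 9-14%. Both rest on assumed fat gain, a median split and visits uniform over 18-30 months. A peak at 24 months roughly halves them, and visits within 22-26 months make them negligible. For Objective 1 no bias is shown, and adjustment there is only a precaution. The change is worth making because it costs almost nothing and replaces a stated rule with a better one.

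**What to change.** 1. Define HFG and LFG on annualised change in total body fat: the Year 2 minus Year 0 difference divided by the exact years between scans.
2. Include exact months between the Year 0 and Year 2 assessments as a covariate in all Objective 2 change models: sedentary behaviour, physical activity, cardiometabolic factors, and the secondary models with visceral and trunk fat.
3. As a precaution, include the same covariate in the Objective 1 change models.

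The cost is analysis-plan wording and about one degree of freedom per model. Scans take place at dated clinic visits and the accelerometer records are already matched on date and time stamps, so no new data, procedures or sample size are needed. If the intervals turn out to be tight, the results will hardly move and nothing is lost.
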